11.2.2 Severity/Intensity

For both AEs and SAEs, the Investigator must assess the severity/intensity of the event.

The severity/intensity of AEs will be graded based upon the subject's symptoms according to the current active minor version of CTCAE, Version 4.03;

Adverse events that are not defined in the CTCAE should be evaluated for severity/intensity according to the following scale:

- Grade 1 = Mild – transient or mild discomfort; no limitation in activity; no medical intervention/therapy required
- Grade 2 = Moderate – mild to moderate limitation in activity, some assistance may be needed; no or minimal medical intervention/therapy required
- Grade 3 = Severe – marked limitation in activity, some assistance usually required; medical intervention/therapy required, hospitalization is possible

- Grade 4 = Life threatening – extreme limitation in activity, significant assistance required; significant medical intervention/therapy required, hospitalization or hospice care probable
- Grade 5 = Death - the event results in death

The term “severe” is often used to describe the intensity of a specific event (as in mild, moderate or severe myocardial infarction); the event itself, however, may be of relatively minor medical significance (such as severe headache). This criterion is not the same as “serious” which is based on subject/event outcome or action criteria associated with events that pose a threat to a subject’s life or functioning.

Seriousness, not severity, serves as a guide for defining regulatory obligations.

11.2.3 Causality

The Investigator must determine the relationship between the administration of study drug and the occurrence of an AE/SAE as Not Suspected or Suspected as defined below:

Not suspected: A causal relationship of the adverse event to study drug administration is unlikely or remote, or other medications, therapeutic interventions, or underlying conditions provide a sufficient explanation for the observed event.

Suspected: There is a reasonable possibility that the administration of study drug caused the adverse event. ‘Reasonable possibility’ means there is evidence to suggest a causal relationship between the study drug and the adverse event.

Causality should be assessed and provided for every AE/SAE based on currently available information. Causality is to be reassessed and provided as additional information becomes available.

If an event is assessed as suspected of being related to a comparator, ancillary or additional study drug that has not been manufactured or provided by Antengene, then the name of the manufacturer when reporting the event will be provided.

11.2.4 Duration

For both AEs and SAEs, the Investigator will provide a record of the start and stop dates of the event.

11.2.5 Action Taken

The Investigator will report the action taken with study drug as a result of an AE or SAE, as applicable (e.g., discontinuation or reduction of study drug, as appropriate) and report if concomitant and/or additional treatments were given for the event.

11.2.6 Outcome

The Investigator will report the outcome of the event for both AEs and SAEs. All SAEs that have not resolved upon discontinuation of the subject’s participation in the trial must be followed until recovered, recovered with sequelae, not recovered or death (due to the SAE).

11.3 Abnormal Laboratory Values

An abnormal laboratory value is considered to be an AE if the abnormality:

- Results in discontinuation from the trial;
- Requires treatment, modification/interruption of study drug dose, or any other therapeutic intervention; or
- Is judged to be of significant clinical importance.

Regardless of severity grade, only laboratory abnormalities that fulfill a seriousness criterion

need to be documented as a serious adverse event.

If a laboratory abnormality is one component of a diagnosis or syndrome, then only the diagnosis or syndrome should be recorded on the AE page/screen of the CRF. If the abnormality was not a part of a diagnosis or syndrome, then the laboratory abnormality should be recorded as the AE. If possible, the laboratory abnormality should be recorded as a medical term and not simply as an abnormal laboratory result (e.g., record thrombocytopenia rather than decreased platelets).

11.4 Pregnancy

All pregnancies or suspected pregnancies occurring in either a female subject or partner of a male subject are immediately reportable events.

11.4.1 Females of Childbearing Potential

Pregnancies and suspected pregnancies (including a positive pregnancy test regardless of age or disease state) of a female subject occurring while the subject is on study drug, or within 28 days of the subject's last dose of study drug, are considered immediately reportable events. study drug is to be discontinued immediately and the subject instructed to return any unused portion of the study drug to the Investigator. The pregnancy, suspected pregnancy, or positive pregnancy test must be reported to Antengene Drug Safety immediately by facsimile, or other appropriate method, using the Pregnancy Initial Report Form, or approved equivalent form.

The female subject may be referred to an obstetrician-gynecologist or another appropriate healthcare professional for further evaluation.

The Investigator will follow the female subject until completion of the pregnancy and must notify Antengene Drug Safety immediately about the outcome of the pregnancy (either normal or abnormal outcome) using the Pregnancy Follow-up Report Form or approved equivalent form.

If the outcome of the pregnancy was abnormal (e.g., spontaneous or therapeutic abortion), the Investigator should report the abnormal outcome as an AE. If the abnormal outcome meets any of the serious criteria, it must be reported as an SAE to Antengene Drug Safety by facsimile, or other appropriate method, within 24 hours of the Investigator's knowledge of the event using the SAE Report Form, or approved equivalent form.

All neonatal deaths that occur within 28 days of birth should be reported, without regard to causality, as SAEs. In addition, any infant death after 28 days that the Investigator suspects is related to the in utero exposure to the study drug should also be reported to Antengene Drug Safety by facsimile, or other appropriate method, within 24 hours of the Investigator's knowledge of the event using the SAE Report Form, or approved equivalent form.

11.4.2 Male Subjects

If a female partner of a male subject taking investigational product becomes pregnant up to 3 months after stopping study drug, the male subject taking study drug should notify the Investigator, and the pregnant female partner should be advised to call her healthcare provider immediately.

11.5 Reporting of Serious Adverse Events

Any AE that meets any criterion for an SAE requires the completion of an SAE Report Form in addition to being recorded on the AE page/screen of the CRF. All SAEs must be reported to Antengene Drug Safety designee within 24 hours of the Investigator's knowledge of the event by facsimile, or other appropriate method, using the SAE Report Form, or approved equivalent form. This instruction pertains to initial SAE reports as well as any follow-up reports.

The Investigator is required to ensure that the data on these forms is accurate and consistent. This requirement applies to all SAEs (regardless of relationship to study drug) that occur during the trial (from the time the subject signs informed consent to 28 days after the last dose of study drug), and those made known to the Investigator at any time thereafter that are suspected of being related to study drug. Serious adverse events occurring prior to treatment (after signing the ICF) will be captured. SAEs should be followed to resolution.

The SAE report should provide a detailed description of the SAE and include a concise summary of hospital records and other relevant documents. If a subject died and an autopsy has been performed, copies of the autopsy report and death certificate are to be sent to Antengene Drug Safety as soon as these become available. Any follow-up data will be detailed in a subsequent SAE Report Form, or approved equivalent form, and sent to Antengene Drug Safety.

Where required by local legislation, the Investigator is responsible for informing the IRB/EC of the SAE and providing them with all relevant initial and follow-up information about the event. The Investigator must keep copies of all SAE information on file including correspondence with Antengene and the IRB/EC.

11.5.1 Safety Queries

Queries pertaining to SAEs will be communicated from Antengene Drug Safety to the site via facsimile or electronic mail. The response time is expected to be no more than five (5) business days. Urgent queries (e.g., missing causality assessment) may be handled by phone.

11.6 Expedited Reporting of Adverse Events

For the purpose of regulatory reporting, Antengene Drug Safety will determine the expectedness of events suspected of being related to study drug based on the Investigator Brochure.

All SUSARs will be reported in an expedited manner in accordance with 21 CFR 312.32.

For participating Asian countries, Antengene or an authorized representative will report in an expedited manner to Regulatory Authorities and Ethics Committees concerned, SUSARs in accordance with Directive 2001/20/EC and the Detailed Guidance on collection, verification and presentation of adverse reaction reports arising from clinical trials on investigational products for human use (ENTR/CT3) and also in accordance with country-specific requirements.

Adverse events such as disease progression, death related to disease progression (in the absence of serious study drug-related events) and serious events due to the relapse of the studied indication will not be subject to expedited reporting by Antengene to regulatory authorities.

Antengene or an authorized representative shall notify the Investigator of the following information:

- Any AE suspected of being related to the use of study drug in this trial or in other studies that is both serious and unexpected (i.e., SUSAR);
- Any finding from tests in laboratory animals that suggests a significant risk for human subjects including reports of mutagenicity, teratogenicity, or carcinogenicity.

Where required by local legislation, the Investigator shall notify his/her IRB/EC promptly of these new serious and unexpected AE(s) or significant risks to subjects.

The Investigator must keep copies of all pertinent safety information on file including correspondence with Antengene and the IRB/EC. (See Section 15.3 for record retention information).

Antengene Drug Safety Contact Information:

For Antengene Drug Safety contact information, please refer to the Serious Adverse Event Report Form Completion Guidelines or to the Pregnancy Report Form Completion Guidelines

12. DISCONTINUATIONS

12.1 Discontinuation from Investigational Product

The following events are considered sufficient reasons for discontinuing a subject from the study drug:

- Adverse Event(s) (that are intolerable)
- Disease progression
- Symptomatic deterioration (global deterioration of health status)
- Physician decision
- Withdrawal by subject (from treatment only)
- Death
- Lost to follow up
- Protocol violation
- Other (to be specified on CRF)

The reason for treatment discontinuation should be recorded in the CRF and in the source documents. Subjects will continue to be followed for post-treatment anticancer therapy and survival status until death.

12.2 Discontinuation from the Trial

The following events are considered sufficient reasons for discontinuing a subject from the trial:

- Death
- Protocol violation
- Lost to follow-up
- Withdrawal of consent for post-treatment follow-up
- Other (to be specified on CRF)

The reason for trial discontinuation should be recorded in the CRF and in the source documents.

At the time of withdrawal, it should be determined if the subject is withdrawing from treatment alone, or from treatment and collection of further data (e.g., survival).

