4. OVERALL STUDY DESIGN

4.1 Study Design

ATG-008-HCC-001 is a MRCT trial in which ATG-008 will be administered orally in HBV+ HCC subjects who have received at least one prior line of systemic therapy in Asian countries. The trial is designed as an open-label phase 2 trial to assess PK, safety, tolerability and efficacy of oral ATG-008 administered until the appearance of radiologic disease progression (according to RECIST 1.1). The PK and safety profiles will be compared with historical ATG-008 results when

data are available.

According to the previous study results, the sponsor will plan to continue to enroll approximately 40 hepatitis B virus (HBV) positive, unresectable HCC subjects who have previously received at least one prior line of systemic therapy. Among which, approximately 20 subjects will receive oral ATG-008 at an initial dose of 45 mg/QD and another 20 subjects will receive oral ATG-008 at an initial dose of 20mg/BID. The pharmacokinetic (PK) samples will be collected from 10 subjects each in the two dose groups so as to further evaluate the PK profile of ATG-008 and its metabolites.

If the overall response rate (ORR) of tumor is greater than 15% in the study dose group (45 mg/QD or 20 mg/BID), then this study will be expanded to enroll additional approximately 110 subjects using ORR as the primary study endpoint, to further evaluate the efficacy and safety of ATG-008.

At the discretion of the Investigator, treatment may continue beyond radiologic progression until symptomatic deterioration if no other therapeutic options are available. Subjects may also receive best supportive care according to local practice. All subjects will continue to be followed after treatment discontinuation for radiologic tumor response until disease progression, death or withdrawal of consent (as defined in Section 6.4, if applicable) and new anticancer treatments until death or withdrawal of consent. Subjects will also be followed for survival until death or withdrawal of consent.

[figure not shown]
The starting dose of ATG-008 will be 15 mg daily for 28 days each cycle for the first 6 fully evaluable (including PK outcomes) subjects. Providing DLTs occur in less than 2 of 6 subjects who complete Cycle 1, additional 24 subjects will be enrolled at the starting dose of 30 mg daily. Subjects who tolerated the 15-mg dose level for at least 1 cycle may then dose-escalate to 30 mg at the Investigator's discretion.

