4.3 Study Duration

The screening period will last up to 28 days. Once treatment begins, subjects will remain on ATG-008 until radiologic disease progression (according to RECIST 1.1), toxicity, subject or physician decision, withdrawal of consent, or death. It is expected that most subjects will receive study drug for 1 to 12 months. If treatment is discontinued for reasons other than disease

progression or death or withdrawal of consent, subjects will be followed for radiologic progression until disease progression. Regardless of treatment status, all subjects will be followed for survival until death or study discontinuation.

According to the previous study results, the sponsor will continue to enroll approximately 40 subjects. Approximately 6 months are needed for enrollment period. Completing PK (PK samples will be collected from 10 subjects each in the two dose groups), safety and preliminary efficacy evaluations is expected to take approximately 6 months.

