8.2.1.1 Treatment Delay

Study drug may be taken up to 12 hours late if dosing has been delayed on a single day; otherwise that day's dose should be omitted and dosing continue on the following day. The subject should never take more than the scheduled dose on any single day.

If study drug is interrupted for more than 21 consecutive days, treatment should be permanently discontinued unless agreed in advance with Antengene.

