19.3 Appendix C: Guidance for Managing Hyperglycemia

Hyperglycemia is a potential class effect of drugs inhibiting mTOR signaling pathways ([Sankhala, 2009](#)). Consequently, this protocol requires close monitoring and early intervention for hyperglycemia.

To detect meaningful incipient hyperglycemia, in Cycle 1 careful review of blood glucose results and possible hyperglycemic symptoms are need during the routine weekly clinic visits. Subjects must also be instructed how to contact study staff immediately in the event of symptoms (eg, polyuria, thirst), in which case prompt assessment in the clinic is necessary.

[figure not shown]
In the event of modest or intermittent hyperglycemia, more frequent monitoring may be required. In the event of persistent fasting hyperglycemia (> 126 mg/dL), or at any time considered appropriate by the Investigator, it is recommended that oral hypoglycemic therapy be initiated. Metformin hydrochloride 464 mg PO nocte is an appropriate starting therapy. It is recommended that dosage be increased by 464 mg every 3 days (or slower in the event of gastrointestinal or other intolerance) to a maximum of 2000 mg. Glucophage, and other biguanide therapy, should be temporarily suspended when planned radiological tumor assessments (e.g., CT scan) involve iodinated contrast (see Section [6.4.1](#)). Subjects should be instructed on how to recognize hypo- and hyperglycemia. Treatment interruptions of > 3 weeks will necessitate removal of the subject from this study.

[Goldberg, 2004](#); [Goldberg, 2005](#); and [Turina, 2006](#) are suggested resources for hyperglycemia management.

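### Appendix C removes a subject from the study after an interruption over 3 weeks where Section 8.2.1.1 stops only the drug, so required follow-up could be lost

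*Combined protocol and SAP*

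**What the plan says.** All references are to the combined protocol and SAP.

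**Long interruptions.** Appendix C (Section 19.3) says that an interruption of more than 3 weeks "will necessitate removal of the subject from this study". It states no exception, and the sentence is not worded for hyperglycemia alone. Section 8.2.1.1, for more than 21 consecutive days, says that "treatment should be permanently discontinued unless agreed in advance with Antengene". It does not mention leaving the study.

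**Follow-up once drug has stopped.** Section 4.1: "All subjects will continue to be followed after treatment discontinuation for radiologic tumor response until disease progression, death or withdrawal of consent". Section 4.3, for stops other than progression, death or withdrawn consent: "subjects will be followed for radiologic progression until disease progression". Section 6.3.2 continues response assessments in the same group. Section 6.4 keeps scans on schedule after a stop for toxicity or by decision of subject or physician. Section 6.3.3 requires survival contact every 8 weeks for everyone until death or loss to follow-up, and the synopsis follows survival to death. Section 4.3 is slightly looser on survival: "Regardless of treatment status, all subjects will be followed for survival until death or study discontinuation".

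**Protocol violations.** Section 12.1 lists them among reasons to stop drug and adds: "Subjects will continue to be followed for post-treatment anticancer therapy and survival status until death". Section 12.2 lists them again under "The following events are considered sufficient reasons for discontinuing a subject from the trial". It closes by asking the site to establish whether a withdrawing subject is leaving treatment only or data collection as well.

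**The concern.** The protocol keeps leaving the drug (Section 12.1) apart from leaving the trial (Section 12.2), so it matters whether a rule says treatment or study. For one trigger, Appendix C uses the second and Section 8.2.1.1 the first. A site cannot apply both literally.

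If a site follows Appendix C, a subject taken off drug for a long interruption may also stop having scans and survival contacts. Section 10.6.2 would then censor that subject at the last date known alive (OS and the 6-, 9- and 12-month survival rates) or at the last progression-free scan (PFS, TTP and DOR). Such censoring may be informative if removed subjects differ in prognosis. If removal comes before the first scan, or before the confirmatory scan in Section 6.4.1, a response may never be documented. The subject still counts in the ORR denominator, because Section 10.2.1 keeps everyone dosed.

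**Working it through.** **1. The plan's own figure.** Section 10.3 gives N = 130 for ORR 10% against 18%, one-sided 0.025, 80% power:

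n = [(1.960·√(0.10·0.90) + 0.842·√(0.18·0.82)) / 0.08]² = 129.8, so 130, with power 80.1%.

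It reproduces and is not in dispute.

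**2. The two rules side by side.**

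| | Appendix C | Section 8.2.1.1 |
|---|---|---|
| Trigger | over 3 weeks | over 21 consecutive days |
| Leaves | the study | treatment |
| Exception | none | prior sponsor agreement |

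The durations are equal and the consequences differ. The synopsis and Sections 4.1, 6.3.2, 6.3.3 and 6.4 all side with Section 8.2.1.1.

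**3. How often.** No rate of interruptions over 3 weeks is given. Two things point to few: Section 8.2.1.2 allows only 2 continuous weeks, and the hyperglycemia row of Table 4, which refers to Appendix C, has no hold step. On the other side, sites will read the appendix. Drug-related hyperglycemia was reported in 45.7% of the first 35 subjects (Section 1.4) and at Grade 3 or above in 24.2% of the first 33 (Section 1.3.2.4). These are not interruption rates.

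**4. Scale for survival.** Suppose k of n subjects are removed alive before month 12 and everyone else's status is known. The 12-month rate is then fixed only to within a range k/n wide. The counts k are assumed.

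- n = 20: k = 1, 2, 3 gives 5, 10, 15 points.
- n = 130: k = 1, 2, 3 gives 0.8, 1.5, 2.3 points.

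The 95% sampling half-width is 1.96·√(p(1−p)/n). With p assumed between 20% and 60%, it is 17.5 to 21.9 points at n = 20 and 6.9 to 8.6 at n = 130. Matching it takes half-width × n removals: 3.5 to 4.4 of 20, or 8.9 to 11.2 of 130. The range k/n measures missing information; it is not a bias.

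**5. Timing against the first scan.** The scan is due at 8 weeks (day 56). Its window opens at 56 − 5 = day 51, or 56 − 7 = day 49 under the wider window also in Section 6.4. An interruption passes 21 days before the window opens if it starts before day 51 − 21 = 30, or 49 − 21 = 28. Whether an end-of-treatment scan would fill the gap is unclear. Section 6.4 mentions one, which may be skipped if the last scan is under 28 days old. Section 6.2.1 says that after a stop without progression no tumor evaluation is needed specifically for that visit.

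**6. Scale for ORR.** One undocumented response lowers the observed ORR by 1/n: 5 points at n = 20, 0.8 at n = 130. If 2%, 5% or 10% of would-be responders were lost this way (pure assumption), a true 18% would be observed as 17.6%, 17.1% or 16.2%. Power, Φ{[(p − 0.10)√130 − 1.960·√0.09] / √(p(1−p))}, would be 77%, 72% or 63%. Nothing in the documents supports any of these shares.

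**The case against.** The best defense is that the intent is plain. Appendix C is guidance, mostly phrased as recommendations, in a translated document, so study may be a loose word for treatment. Interruption is not a named reason in Section 12.2. Neither passage tells a site to stop scans or survival contact. Section 4.3's reference to study discontinuation fits withdrawn consent or loss to follow-up just as well. All of this is fair, and it makes literal use of Appendix C less likely. It does not remove the mismatch: the sentence is mandatory, allows no exception, and uses a term that the protocol elsewhere distinguishes from stopping drug.

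A reader might infer that Sections 12.1 and 12.2 contradict each other on protocol violations. The documents do not support that. The lists serve separate decisions, and death, loss to follow-up and other reasons also appear in both. Section 12.2 says what is sufficient, not what is required, and its last sentence asks whether only treatment is ending. What remains is narrower: no rule decides the case, so a site may end follow-up of a dosed violator whom Section 6.3.3 would keep.

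The objection that the trigger is rare also stands, and it sets the priority.

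**Conclusion.** The mismatch between Appendix C and Section 8.2.1.1 is real, and the rest of the plan shows which way to resolve it. The consequence is possible, avoidable loss of follow-up in a probably small number of subjects. It falls mainly on secondary endpoints, for which Section 10.6.2 names no test.

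A reader might infer that the Kaplan-Meier estimates are biased or that the ORR test is underpowered. Neither follows. The documents give no frequency of such removals and no prognosis for the subjects concerned, so neither size nor direction of bias can be derived. The figures under steps 4 and 6 show scale under assumed counts only. The opposite reading, that ORR cannot be touched, is also too strong: the hypotheses, N and denominator stand, but a response lost before a first or confirmatory scan would count as non-response.

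Section 12.2 is a secondary point about a missing rule. Overall priority is low.

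**What to change.** **Appendix C.** Replace "will necessitate removal of the subject from this study" with: *will require permanent discontinuation of study drug; tumor and survival follow-up continue per Sections 6.3.2 and 6.3.3.* This takes no position on the interruption limit or the sponsor exception. The 2 weeks in Section 8.2.1.2 against 21 days in Section 8.2.1.1 is a separate matter to settle.

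**Section 12.2.** Add: *A protocol violation in a dosed subject stops study drug only; follow-up continues unless consent is withdrawn or invalid.* Leave the open category for other reasons as it is, since some exits cannot be foreseen.

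**Cost.** A few words in two places. Removal cannot come before an interruption has lasted 21 days, so each subject kept adds at most 6 survival contacts to month 12: (365 − 21)/56 = 6.1. Scans to progression number about 2: 1/(1 − 0.5^(1.84/2.0)) = 2.1, with 8 weeks = 1.84 months, exponential PFS assumed, and the median of 2.0 months from Section 1.3.2.4 (15 and 30 mg groups). Over that median's confidence interval, 1.9 to 3.8 months, the figure is 2.1 to 3.5. The protocol already plans this follow-up for other subjects who stop treatment.
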